1. SYNOPSIS

Study Title:	Vitamin D Levels in Subjects with Vitamin D Deficiency Following Topical Application of Vitamin D Gel – A Proof of Concept Study
Protocol Number:	VITD-001
Development Phase:	Phase 1
Indication:	Subjects with known vitamin D deficiency (<20 µg/L Total 25-OH Vitamin D)
Study Drugs: (Including test, comparator, dosage form, dosing regimen and route)	
A novel vitamin D₃ (cholecalciferol) is provided as a topical gel using ingredients that are identified in the USP/NF and/or designated in the list of Inactive Ingredients in FDA Approved Drugs. The ingredients in the topical gel are well known in the industry and have references in the pharmaceutical literature and some have available FDA drug master file information. A single applicator contains 0.75g of gel, containing 150,000 international units of vitamin D3 (cholecalciferol) to be applied to the upper arm. One dose consists of two applicators, one applied to each upper arm, for a total of 300,000 international units per dose.
 
Subjects with known vitamin D deficiency of ≤20 ng/ml total 25-OH Vitamin D (50 nmol/liter) will be consented and enrolled. They will have a blood draw prior to dosing on Day 1 (to obtain a baseline vitamin D, calcium, albumin, and parathyroid hormone level) and will receive 300,000 units of topical vitamin D3. On Day 7, subjects will return to the clinic for a blood draw to assess Vitamin D level and to check for any signs of skin rash and/or reaction. If a subject has a skin rash and/or reaction prior to Day 7, he/she will be advised to return to the clinic for assessment as soon as possible. Any rash and/or skin reaction may be photographed and diagnosed. A second dose of 300,000 units of topical Vitamin D will be applied by the nurse at the day 7 visit. Subjects will return on Day 14 for a third dose and a third blood draw. A final blood draw to assess for Vitamin D level will be done on day 21.
 
A study nurse or physician will apply each dose of topical Vitamin D. Prior to application of the gel, 2 strips of paper tape will be applied to the subject's upper arms. One strip will be applied approximately 2 inches below the subject's shoulder and the second strip will be applied approximately 2 inches above the subject's elbow. The entire contents of one syringe (0.25 mL of gel) will be applied onto the subjects arm in a straight line, from approximately 1 inch below the first strip of paper tape to approximately 1 inch above the second strip of paper tape. The subject will be instructed to gently rub the gel into their upper arm with their fingertips, while staying between the two pieces of paper tape, for approximately 2 minutes or until the gel has been absorbed. After completing the application process on both arms, the subject will wash his/her hands thoroughly.

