
Safety
	
All subjects will be monitored for skin rash or other reactions. Any rash and/or reaction will be photographed by study staff and assessed/diagnosed by a physician.
 
Patient will have serum calcium followed each week during the study. Although it is unlikely that calcium will change with an increase in topical Vitamin D, hypercalcemia presents a potential theoretic risk if absorption is high or unexpected variability in vitamin D absorption exists.

Laboratory Parameters/Analysis:
	
Laboratory analyses will consist of 25-hydroxyvitamin D blood levels (D2 and D3) and parathyroid hormone levels. For safety, an albumen adjusted calcium determination will be measured on day 0, 7, 14, and 21.

Total Blood Volume:
	
Approximately 5 mL will be required at day 0, 7, 14, and 21 to assess for vitamin D parameters and safety.

Sample Size Determination: (If applicable)	The study will have 20 subjects who are evaluable for changes in vitamin D blood levels.
Statistical Analyses: (Brief Description)	Two sample paired t test of pre and post total vitamin D and parathyroid hormone with an alpha of .05. We do not expect any significant change in adjusted calcium.

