10.3 Study Drug Administration

A study nurse or physician will supervise each treatment application to ensure that the gel is applied correctly. Prior to application of the gel, 2 strips of paper tape will be applied to the subject's upper arms. One strip will be applied approximately 2 inches below the subject's shoulder and the second strip will be applied approximately 2 inches above the subject's elbow. The entire contents of one syringe (0.75 mL of gel) will be applied onto each arm in a straight line, from approximately 1 inch below the first strip of paper tape to approximately 1 inch above the second strip of paper tape. The subject will be instructed to gently rub the gel into their upper arm with their fingertips, while staying between the two pieces of paper tape, for approximately 2 minutes or until the gel has been absorbed. After completing the application process on both arms, the subject will wash his/her hands thoroughly.

Handling and Storage of Study Drug

Specific instructions for preparing and administering the topical vitamin D gel are provided in Appendix 1.

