11.1 Baseline Assessments

A chart review of subjects with known vitamin D deficiency will be performed prior to Day 0 in order to assess for potential study eligibility. Informed consent must be obtained before any study procedures are performed.

11.1.1 Study Day 0

The following procedures should be completed on Day 0:

- informed consent
- assessment of height, weight and skin to assess for study eligibility
 - Anthropometric Assessment
 - Patients are measured for height (cm) and weight (kg) following standardized procedures as outlined in the Anthropometric Standardization Reference Manual (Lohman et al., 1991). Body weight is measured with a stand-on digital scale and height is measured by a stadiometer. Height is measured to the nearest 0.1 cm and weight to the nearest 0.1 kg.
 - Recording of Fitzpatrick skin-type score.
- Blood draw for vitamin D level, parathyroid hormone level, calcium, and albumin.
- Application of the topical vitamin D gel, including instructions for dosing at home

11.1.2 Study Day 7 and Study Day 14

- Evaluation of skin site where gel applied. If the subject has any skin rash or other reaction, he/she should contact study personnel as soon as possible for photographs and an assessment/diagnosis
 - Photographs of application sites
 - A digital photograph may be taken of the gel application site following application to record any signs of irritation or reaction. Identifying marks on or near the application site (i.e. tattoos, birthmarks, scars etc.) should be avoided when a photograph is taken. Digital photographs will be uploaded to the REDcap database and stored on the secure server.
- Blood draw for vitamin D level and calcium
- Application of the topical vitamin D gel

11.1.3 Study Day 21

- Assessment of skin for rash or any other reaction
- Blood draw for vitamin D, parathyroid hormone level, and calcium.

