13. ASSESSMENT OF SAFETY

13.1 Safety Assessments

13.1.1 Skin Rash or Other Reaction

An assessment of each subject's skin will be performed on Days 7, 14 and 21 using the following scoring system for topical irritation developed per FDA guidance:

Basic Score: Description:

- 0 No visible reaction
- 0.5 Doubtful or negligible erythema reaction
- 1.0 Mild or just perceptible macular erythema reaction in a speckled/follicular, patchy or confluent pattern (slight pinking)
- 2.0 Moderate erythema reaction in a confluent pattern (definite redness)
- 3.0 Strong or brisk erythema reaction that may spread beyond the test site

Supplemental Scores: Description: Label:

- 0.5 Edema E
- 0.5 Papules P
- 0.5 Vesicles V
- 0.5 Bullae B

Supplemental scores will be added to the basic scores if the associated symptoms are present. The final score will be the sum of the basic and supplemental scores.

As part of the general safety assessment, dermal irritation will be evaluated by the Investigator or designated research staff using the outlined scale. The likelihood of allergic reaction not manifested as a dermal irritation is extremely low. Given that all the ingredients used to make the topical vitamin D gel are considered GRAS, we do not anticipate non-local allergic reactions. In the event that a non-dermal allergic reaction occurs, standard medical procedures utilized for such situations will be followed.

If a subject develops a dermal response of 1.5 up to 2.5, he or she will be given the option to permanently discontinue the study treatment and withdraw from the study, or to allow sufficient time for the rash to resolve before he or she reinitiates the phase of the study he or she was in at the time that the rash developed. If a participant develops a dermal response of 2.5 or greater, he or she will be required to permanently discontinue the study treatment and he or she will be withdrawn from the study. In both cases, the study participant will be encouraged to seek medical care from his or her primary care physician. In addition, we will ask subjects who decide to withdraw from the study to return for their next scheduled blood draw, as per protocol. We will also follow up with any study participant who withdraws from the study due to AE occurrence through telephone contact at 1 week intervals until the AE resolves.

All other adverse events will be assessed by self-report from subjects.

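### The dose-hold and withdrawal steps in Protocol 13.1.1 depend only on the summed skin score, so one blister sign with doubtful redness (1.0) requires no hold, and a total of exactly 2.5 falls in both action bands.

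*Protocol*

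**What the plan says.** Protocol 13.1.1 gives a redness grade of 0, 0.5, 1, 2 or 3 and four supplemental signs (edema, papules, vesicles, bullae) worth 0.5 each. "The final score will be the sum of the basic and supplemental scores".

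Two bands of that total carry a consequence for treatment:

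- Lower band: "If a subject develops a dermal response of 1.5 up to 2.5, he or she will be given the option to permanently discontinue" treatment and withdraw, or to "allow sufficient time for the rash to resolve before he or she reinitiates the phase of the study he or she was in".
- Upper band: "If a participant develops a dermal response of 2.5 or greater, he or she will be required to permanently discontinue the study treatment".

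In both bands the subject is also encouraged to see a primary care physician. Nothing about dosing is stated for totals below 1.5, and no step depends on which sign is present.

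The skin check and the next dose share a visit. The Synopsis states "A second dose of 300,000 units of topical Vitamin D will be applied by the nurse at the day 7 visit". Protocol 11.1.2 lists, for Days 7 and 14, an evaluation of the application site, a blood draw, and then "Application of the topical vitamin D gel", with no condition linking the first to the last. Protocol 10.3 puts each application on the same part of the upper arm, marked off with tape: "The entire contents of one syringe (0.75 mL of gel) will be applied onto each arm in a straight line".

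Some handling applies at any score. The Safety row of the Synopsis says "Any rash and/or reaction will be photographed by study staff and assessed/diagnosed by a physician". Protocol 13.2.3 requires each adverse event to be recorded with the action taken, and Protocol 8.3 lists a skin reaction among possible reasons for removal from treatment.

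**The concern.** A rule for withholding gel from a reacting site should not let blistering pass while it stops a reaction made up of lesser signs. Because every sign carries the same 0.5 and only the total counts, the rule in 13.1.1 can do this. Staff could re-apply gel to an arm with vesicles or bullae at the Day 7 or Day 14 visit and be fully compliant, while a subject with doubtful redness, edema and papules would have to be offered the choice to stop or wait. Action in the first case rests on discretion alone.

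The second matter is one of drafting. The value 2.5 closes the lower band and opens the upper one, so at that total the text supports both an optional and a mandatory stop.

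At stake is the handling of individual subjects in a Phase 1 study whose secondary objective is safety, including skin reactions.

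**Working it through.** **Inputs**, all from Protocol 13.1.1: redness grades 0, 0.5, 1, 2, 3; 0.5 for each of edema (E), papules (P), vesicles (V), bullae (B); action bands starting at 1.5 and at 2.5.

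**Formula:** total = redness grade + 0.5 × number of signs present.

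**Individual cases**

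| Redness | Signs | Total | Step in 13.1.1 |
|---|---|---|---|
| 0.5 | V | 0.5 + 0.5 = 1.0 | none |
| 0.5 | B | 0.5 + 0.5 = 1.0 | none |
| 0.5 | E, P | 0.5 + 1.0 = 1.5 | offer to stop or wait |
| 1.0 | P | 1.0 + 0.5 = 1.5 | offer to stop or wait |
| 0.5 | V, B | 0.5 + 1.0 = 1.5 | offer to stop or wait |
| 2.0 | any one sign | 2.0 + 0.5 = 2.5 | both bands |

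Both choices in the lower band mean that no gel goes on at that visit, so 1.5 is in effect the threshold for a hold.

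**How many patterns are missed.** Four signs give 2⁴ = 16 subsets, of which 16 − 4 = 12 contain V or B.

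- *Narrow reading:* redness 0 is not used when a sign is visible. There are 4 × 12 = 48 patterns with V or B. At redness 0.5 a total below 1.5 allows only one sign, hence V or B alone. At redness 1 or more, one sign already gives at least 1.5. Missed: 2 of 48.
- *Wide reading:* signs may be added to redness 0. There are 5 × 12 = 60 patterns. Redness 0 adds the patterns with one or two signs: V, B, EV, EB, PV, PB, VB, which is 7. Missed: 2 + 7 = 9 of 60.

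**How many patterns total exactly 2.5.** Redness 0.5 with all four signs (1), redness 1 with any three (4), redness 2 with any one (4): 1 + 4 + 4 = 9. Of these, 1 + 4 + 2 = 7 include V or B. The count is the same under both readings, because redness 0 reaches at most 2.0.

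**After the changes proposed below:** missed patterns are 0 of 48 and 0 of 60, and no pattern lies in both bands.

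**The case against.** **Something does happen at a total of 1.0.** A reader might infer that a blister with doubtful redness is ignored. The documents do not support that. The Safety row of the Synopsis calls for a photograph and a physician's assessment of any reaction, 13.2.3 requires an adverse-event record and follow-up, 8.3 allows removal or withdrawal at any score, and 14.3.3 provides for missed doses. This stands, and it limits the point to the absence of a required hold or a required offer to stop or wait. It does not close the gap. None of these provisions says that assessment must precede the same-visit application or that gel is withheld. Another row of the Synopsis makes the photograph and diagnosis optional. Protocol 8.3 concerns removal, not a temporary hold.

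**The ranking of signs is a clinical judgement.** The protocol weights all four signs equally and says the scale follows FDA guidance, which cannot be consulted here. The equal weighting therefore cannot be called an error. That vesicles or bullae deserve at least as much caution as edema with papules is a judgement brought to the text. The proposed change leaves the scale and its sum alone.

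**The gap is narrow.** On the narrow reading 46 of 48 patterns with vesicles or bullae already trigger a step. That is correct and keeps the point minor.

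**The overlap at 2.5 reads naturally as excluding 2.5 from the lower band.** This is probably the intent, but the wording does not say so, and moderate redness with a single sign is enough to reach that total.

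**Nothing statistical turns on it.** A reader might infer bias in the skin-reaction endpoint. There is none from this source: Protocol 14.2 counts subjects with any skin reaction, so a blister is counted whatever its total.

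**Conclusion.** The point holds as a minor correction to a safety rule. Vesicles alone or bullae alone with doubtful redness total 1.0 and require neither a dose hold nor the offer of one, although edema plus papules at the same redness do require the offer. This affects 2 of 48 patterns with vesicles or bullae, or 9 of 60 if signs may be added to redness 0. Separately, 9 patterns total exactly 2.5 and fall in both bands.

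The arithmetic uses only the protocol's scores. The recommendation assumes that blistering merits at least the caution already given to a total of 1.5. The counts are of possible score patterns. The documents give no rate of blistering, so no expected number of affected subjects can be stated. Endpoints and analyses are unchanged.

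**What to change.** Keep the scale and the sum, and change two things in Protocol 13.1.1:

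1. Add: *Any vesicle or bulla at an application site, whatever the total, is handled at least as a response of 1.5. The subject is offered the option to stop or to wait until resolution and is advised to seek medical care. No gel is applied at that visit.*
2. Write the lower band as *1.5 to less than 2.5*, so that exactly 2.5 is a mandatory stop only.

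The cost is a few sentences. Vesicles and bullae are already scored, so no new data are needed. The first change adds an action for 2 of the 65 patterns on the narrow reading (4 × 16 = 64, plus redness 0 with no sign) or 9 of 80 on the wide one (5 × 16). The downside is that a dose will occasionally be delayed for a trivial vesicle. How later doses and draws are timed after a wait is a separate question that the existing 1.5 band already raises, and this change does not try to settle it.

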Of all of the forms of vitamin D, cholecalciferol (Vitamin D3) has been viewed as having the best overall combination of safety and efficacy, assuming normal kidney and liver function. In the US, cholecalciferol has primarily been available as an oral supplement at fairly low doses (most commonly 1000 – 2000 IU). In otherwise healthy patients, a common US standard of care for treatment of low serum vitamin D is to give 50,000 IU Vitamin D orally per week for four weeks (total dose 200,000 IU) until levels are brought up into the adequate

[figure not shown]

Figure 1. Absorption kinetics of oral Vitamin D3.

effective long term treatment of vitamin D deficiency. The proposed study aims to investigate both safety and efficacy of a topically applied vitamin D that is likely to be more effective, convenient, or acceptable for many individuals.

A wide variety of dosing schedules for Vitamin D have been documented¹⁸. Recently Vieth's team conducted a study with oral cholecalciferol in 48 elderly women (81 ± 8 years)¹⁹. The study tested oral cholecalciferol (D3) up to 45,000 IU once every 28 days. The study showed that a single oral dose of 45,000 IU dissolved in alcohol generally produced a rise in serum vitamin D of about 10 ng/ml. A second oral dose 28 days later further increased the serum vitamin D level by about another 10 ng/ml. Thus, the total increase after two oral doses (90,000 IU) was about 20 ng/ml. Although following oral dosing, rises in serum Vit D can be seen up to one month following administration, Vieth's study demonstrated that most of the rise (>60%) in Vitamin D occurs within 7 days. (Figure 1). No one receiving oral monthly dosing of 45,000 IU Vitamin D3 developed hypercalcemia.

Vitamin D Product Development

Innovative Pharmacy Services, Inc. has developed a vitamin D3 topical gel using ingredients that are identified in the USP/NF and/or designated in the list of Inactive Ingredients in FDA Approved Drugs. The ingredients in the topical gel are well known in the industry and have references in the pharmaceutical literature and some have available FDA drug master file information. A single applicator contains 0.75 g of gel, containing 150,000 international units of vitamin D3 (cholecalciferol). One dose will consist of two applicators. One applicator will be applied to each of the subject's upper arm for a total dose of 300,000 units.

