8.3 Criteria for Withdrawal

A subject has the right to withdraw fully or partially from the study at any time and for any reason without prejudice to his or her future medical care by the physician or at the institution.

Withdrawal of full consent for a study means that the subject does not wish to receive further investigational treatment and does not wish to or is unable to continue further in study participation. Subject data up to withdrawal of consent will be included in the analysis of the

study. The Investigator will discuss with the subject appropriate procedures for withdrawal from the study. Withdrawal of partial consent from a study means that the subject does not wish to take investigational product or other protocol-required therapy any longer but is still willing to collaborate in providing further data by continuing on study. Should a subject request or decide to withdraw from the study, all efforts will be made to complete and report the observations as thoroughly as possible up to the date of withdrawal. All information should be reported on the applicable case report form (CRF). Reasons for removal from protocol-required treatment or observation might include:

- partial/full withdrawal of consent
- administrative decision by the Sponsor-Investigator
- pregnancy
- ineligibility
- significant protocol deviation
- subject noncompliance
- adverse event, including rash or other skin reaction
- Death

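### Section 13.1.1 ties stopping gel for a skin reaction to leaving the study and requests one more blood draw, so subjects stopped before the Day 14 draw are not asked for Day 21 vitamin D, calcium or PTH

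*Protocol*

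**What the plan says.** Protocol section 13.1.1 sets two routes by dermal score. At 1.5 up to 2.5 the subject is "given the option to permanently discontinue the study treatment and withdraw from the study", or may wait for the rash to resolve and resume. At 2.5 or greater, "he or she will be required to permanently discontinue the study treatment and he or she will be withdrawn from the study". The paragraph continues "In both cases, the study participant will be encouraged to seek medical care" and then adds that "we will ask subjects who decide to withdraw from the study to return for their next scheduled blood draw, as per protocol". Anyone who withdraws because of an adverse event is also telephoned weekly until it resolves.

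Section 8.3 separately defines partial withdrawal: a subject no longer wishes to take product but "is still willing to collaborate in providing further data by continuing on study". Section 13.1.1 does not refer to it.

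Table 1 puts doses on Days 0, 7 and 14, vitamin D and calcium on Days 0, 7, 14 and 21, and PTH on Days 0 and 21 only. The synopsis says "Patient will have serum calcium followed each week during the study". Sections 1 and 6 place calcium and PTH within the safety objective.

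A subject who stops early for a drug-related adverse event stays in the Efficacy Evaluable Population (protocol 14.1, SAP 1.1) and is not replaced (8.4). Missing values are not imputed (protocol section 14, SAP section 1). The primary endpoint is the change following three doses (protocol 14.2, SAP 1.2).

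**The concern.** Stopping treatment and stopping observation are separate decisions, and 13.1.1 makes them one. The subjects concerned are those who react to the product, whose remaining laboratory follow-up a first study of a new topical formulation should want. Because the request is for a single draw, the timing of the reaction decides which safety measurements are sought.

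Two things would be lost. One is weekly calcium to Day 21, which the synopsis promises without an exception for early stops. The other is PTH, which has no post-dose measurement except Day 21.

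Timing matters because vitamin D can go on rising after the last dose. Section 5.1 says that "following oral dosing, rises in serum Vit D can be seen up to one month following administration", although "most of the rise (>60%) in Vitamin D occurs within 7 days". A last draw 7 days after the last dose could therefore miss part of the rise, if the oral pattern carried over to the gel.

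**Working it through.** The plan gives no figure for this point, so the check applies the next-draw rule to the schedule.

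**Inputs.** Doses on Days 0, 7 and 14; post-dose draws on Days 7, 14 and 21; post-dose PTH on Day 21 only (Table 1, sections 7.1 and 11.1). On the natural reading, the next draw is requested in both routes and later draws are not.

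**Draws requested.** Days since last dose = day of last requested draw minus day of last dose.

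| Gel stopped | Doses | Draw requested | Vitamin D and calcium draws not requested | Day 21 PTH | Last draw after last dose, now | With the fix |
|---|---|---|---|---|---|---|
| Before Day 7 draw | 1 | Day 7 | 2 (Days 14, 21) | not requested | 7 − 0 = 7 days | 21 − 0 = 21 days |
| Day 7, after draw, before dose 2 | 1 | Day 14 | 1 (Day 21) | not requested | 14 − 0 = 14 days | 21 − 0 = 21 days |
| After dose 2, before Day 14 draw | 2 | Day 14 | 1 (Day 21) | not requested | 14 − 7 = 7 days | 21 − 7 = 14 days |
| After Day 14 draw | 2 or 3 | Day 21 | 0 | requested | unchanged | unchanged |

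Sections 1 and 11.1.2 list the skin assessment before the blood draw at the Day 7 and Day 14 visits. If visits run in that order, a reaction first found at Day 14 makes that day's draw the next one, and the third row applies. Listing order does not prove the sequence.

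**Oral kinetics.** More than 60% of the rise comes within 7 days, so up to 100 − 60 = 40% could come later. Topical kinetics are unknown.

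**Number affected.** No reaction rate is given. Assume a proportion r of the 20 subjects stop for a skin score before the Day 14 draw. Expected number = 20r; chance of at least one = 1 − (1 − r)^20.

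- r = 1%: 0.2 subjects; 1 − 0.99^20 = 18%
- r = 2%: 0.4 subjects; 1 − 0.98^20 = 33%
- r = 5%: 1.0 subject; 1 − 0.95^20 = 64%

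**Primary endpoint if early-stop values are pooled.** Assume a linear dose effect and 10 µg/L after three doses, so 3.33 after one dose and 6.67 after two.

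- One one-dose subject in 20: (19 × 10 + 3.33)/20 = 9.67, lower by 0.33 µg/L
- One two-dose subject in 20: (19 × 10 + 6.67)/20 = 9.83, lower by 0.17 µg/L
- Two one-dose subjects in 20: (18 × 10 + 2 × 3.33)/20 = 9.33, lower by 0.67 µg/L

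Collecting Day 21 values from early stops therefore calls for a rule on how they enter the primary summary.

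**The case against.** The strongest case against has four parts.

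**Other provisions cover the gap.** Section 8.3 lets a willing subject stop product and keep giving data. Section 13.2.3 requires adverse events to be followed and allows additional laboratory tests. This stands in part. A reader might infer that the protocol bars Day 21 data from reacting subjects; it does not, and one draw is what 13.1.1 requests rather than a ceiling. But 8.3 is framed by the subject's own wish, which does not clearly fit a mandatory stop, and the tests in 13.2.3 are discretionary. Neither schedules a Day 21 draw.

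**The safety stake is small.** These subjects have had one or two doses. Section 5.2.2 reports that 300,000 IU in total, the amount in one present dose, produced an average change it calls insignificant in three subjects. The protocol describes a calcium change as unlikely and hypercalcemia as a theoretic risk. PTH is there to show the effect of correction, which one or two doses may not achieve. This stands, and it is why the gap is called modest.

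**The primary result is hardly touched.** A reader might infer bias in the primary endpoint. The documents do not support that: the endpoint is change following three doses, which these subjects have not had, and the analysis in section 14 is descriptive, without p-values.

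**A careless fix does harm.** Simply deleting study withdrawal would remove the trigger for weekly telephone contact, which applies to subjects who withdraw because of an adverse event. It would also let one- and two-dose values dilute the main mean. Both objections are right, and the change proposed here deals with them.

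A last tempting reading is that mandatory stops are asked for no blood at all, because the request is addressed to subjects who decide to withdraw. The sentence follows directly on text covering both cases, so the natural reading includes them. The wording is unclear rather than an exclusion.

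**Conclusion.** The point holds as a modest gap in safety and laboratory follow-up. A subject stopped before the Day 14 draw is not asked for Day 21 vitamin D, calcium or PTH, and one or two of the three post-dose draws go unrequested. Nothing is lost for a stop after the Day 14 draw, or for a subject who waits and resumes.

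This rests on reading the next-draw request as covering both routes, and on the subject not taking up partial withdrawal unprompted. The number affected is unknown; the 18% to 64% chance of at least one follows only from the assumed 1% to 5%. The 40% figure is an upper bound from oral dosing. The effect on the primary endpoint is minimal. The rule against replacing drug-related stops is reasonable and is not in question.

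**What to change.** Four wording changes:

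1. In 13.1.1, remove study withdrawal from both routes, so that subjects stop gel but stay on study unless they withdraw full consent, with a reference to 8.3.
2. Replace the next-draw sentence with: *Every subject who stops gel for a skin reaction, by choice or by requirement, will be asked to attend all remaining scheduled visits through Day 21 (skin score, 25-OH vitamin D, calcium, and Day 21 PTH).*
3. Reword the telephone sentence to cover any participant who *discontinues study treatment or withdraws from the study due to AE occurrence*, so that weekly contact until resolution is kept.
4. In protocol 14.3.5 and SAP 1.3.5, make the Day 21 change in subjects who received all three doses the main summary, with the whole Efficacy Evaluable Population shown alongside.

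The score thresholds, the option to wait and resume, the replacement rule and the population definitions stay as they are. The cost is an amendment, one or two extra attendances by each affected off-gel subject at visits already scheduled, and one extra descriptive summary. No new visit or type of test is needed.
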